## 4.3 Treatment period

#### 4.3.1 Randomisation and baseline visit (Visit 2, Week 0)

Visit 2 (Randomisation/Baseline) should take place approximately 2 weeks after Visit 1. Prior to this visit, patients are to have fasted overnight (8 to 12 hours). Patients are advised to refrain from alcohol intake and intense exercise 24 hours prior to each visit and recommend not to use tobacco/nicotine within 12 hours prior to each visit. Patients should delay administering their morning dose of metformin on the morning of the study site visit.

The following will be performed during this visit:

1. Inclusion/exclusion and randomisation criteria will be verified.

- 2. Patients will be randomly assigned to 1 of 3 treatment groups (while continuing on metformin therapy) by IVRS/IWRS:
  - Dapagliflozin 5mg + saxagliptin 5mg
  - Dapagliflozin 5mg + placebo for saxagliptin
  - Saxagliptin 5mg + placebo for dapagliflozin
- 3. A brief physical examination may be conducted at Investigators discretion (see Section 5.2.2).
- 4. Vital signs (sitting systolic and diastolic BP and Heart Rate) will be measured (see Section 5.2.3).
- 5. Body weight will be measured Section 5.1.3.
- 6. Concomitant medications (including over the counter and herbal/nutritional supplements) will be reviewed.
- 7. Blood samples will be collected prior to administration of study medication for the following assessments:
  - Clinical chemistry and Hematology (see Section 5.2.1)
  - HbA1c
  - eGFR (MDRD)
  - FPG (samples for central laboratory testing, see Section 5.2.1)

#### CC

- 8. Urine will be collected for following (see Section 5.2.1)
  - Urinalysis
  - Urinary pregnancy test for beta human chorionic gonadotropin (βhCG) for female patients (WOCBP only)
- 9. AEs and SAEs will be reviewed.
- 10. Diet and Exercise counseling will be provided.
- 11. Glucose meter and/or supplies and instructions will be provided.
- 12. Patient diary and instructions will be provided.

- 13. Patient diary will be reviewed for glucometer values and/or hypoglycaemic events history.
- 14. Study medication will be dispensed. Study site personnel will monitor administration of study medication and morning dose of metformin with food.

## 4.3.2 Treatment period visits (Visits 3 and 4; Weeks 6 and 12)

Prior to these visits, patients are required to have fasted overnight (8 to12 hours). Patients are advised to refrain from alcohol intake and intense exercise 24 hours prior to each visit and recommend not to use tobacco/nicotine within 12 hours prior to each visit. Patients should delay administering their morning dose of metformin and study medication on the morning of the study site visits. Patients should bring their metformin and study medication with them to the study site and will self-administer study medication as directed by study-site personnel.

The following will be performed during these visits:

- 1. A brief physical examination may be conducted at Investigators discretion (see Section 5.2.2).
- 2. Vital signs (sitting systolic and diastolic BP and Heart Rate) will be measured (see Section 5.2.3).
- 3. Body weight will be measured Section 5.1.3.
- 4. Concomitant medications (including over the counter and herbal/nutritional supplements) will be reviewed.
- 5. Blood samples will be collected prior to administration of study medication for the following assessments:
  - Clinical chemistry (see Section 5.2.1)
  - Hematology except Visit 3 (see Section 5.2.1)
  - HbA1c
  - eGFR (MDRD)
  - FPG (samples for central laboratory testing, see Section 5.2.1
- 6. Urine will be collected for urinalysis.
- 7. AEs and SAEs will be reviewed.
- 8. Patient diary will be reviewed for glucometer values and/or hypoglycaemic events history

- 9. Diet and Exercise counseling will be provided.
- 10. Glucose meter and/or supplies and instructions will be provided.
- 11. Patient diary and instructions will be provided.
- 12. Study medication will be dispensed and returned (except Visit 3). Study site personnel will monitor administration of study medication and morning dose of metformin with food.
- 13. Study medication compliance will be reviewed
- 14. Rescue medication will be dispensed (as necessary, see Table 1)

## 4.4 Rescue therapy

During the double-blind treatment period of the trial, patients may be eligible for treatment with open-label rescue medication (see Table 6) to replace their blinded treatment regimen in order to treat ongoing hyperglycaemia. The sub-sections and table listed below define the lack of glycaemic control criteria for initiation of rescue medication.

Pre-specified glycaemic criteria (see Table 2), based upon repeat confirmatory central laboratory FPG have been established during the double-blind treatment period, starting at

Table 2 Criteria for Initiation of Rescue Therapy During the Randomised Treatment Period

Visit Period	Central Laboratory glycaemic parameters		
At Week 6	FPG >270mg/dL (15.0mmol/L)		
From Week 6 to Week 12 (Excluding Week 12)	FPG > 240 mg/dL (13.3 mmol/L)		
Week 12 to Week 24	FPG > 200mg/dL (11.1mmol/L)		

Week 6, to determine eligibility for open-label rescue medication.

Abbreviations: FPG Fasting plasma glucose

Patients with a central laboratory FPG value meeting the lack of glycaemic control criterion at a pre-specified visit will be scheduled for a follow-up visit (within 3 to 5 days) to obtain a second central laboratory FPG value and review the patients glucose meter readings. If the repeat central laboratory FPG value still meets the criterion, the patient must be rescued.

Patients who meet rescue criteria in the double-blind treatment period must first complete the Rescue Visit procedures before receiving open-label rescue medication to ensure that important trial endpoint measurements are collected.

Following completion of the Rescue Visit, rescued patients will be given open-label antidiabetic rescue medication (Saxagliptin 5mg and Dapagliflozin 10 mg as a first line or Insulin as a second line at Investigators discretion) and will discontinue study medication. Rescued patients will then continue in the double-blind treatment period according to their original visit schedule.

Note: Rescue medication (Saxagliptin 5mg and Dapagliflozin 10mg) will be provided by Sponsor in this study. Insulin will not be provided by Sponsor since it is part of patients standard of care.

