The recommended starting dose of dapagliflozin is 5mg in a few countries. The dose can be increased to 10mg in patients tolerating dapagliflozin 5mg who require additional glycaemic control. The aim of this study is thus to provide relevant clinical data regarding the efficacy and short term safety of saxagliptin 5mg co-administered with dapagliflozin 5mg after 24 weeks.

This is a double-blind, randomised, active-controlled, multi-center, 24 week, parallel-group study to evaluate safety and efficacy of saxagliptin 5mg co-administered with dapagliflozin 5mg, compared with either saxagliptin 5mg or dapagliflozin 5mg all given as add-on therapy to metformin in patients who are inadequately controlled on metformin alone. After randomisation the patients will visit the clinic after 6, 12, and 24 weeks. Efficacy as well as safety assessments will be taken before randomisation and at each visit at the clinic.

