#### 3.1 Inclusion criteria

For inclusion in the study patients should fulfil the following criteria:

- 1. **Signed written informed consent:** Patients must be willing and able to give signed and dated written informed consent.
- 2. Target population:
- (a) Patients with T2DM with inadequate glycaemic control, defined as a central laboratory HbA1c  $\geq$ 7.5% to  $\leq$ 10.0% obtained at the screening visit.
- (b) Fasting Plasma Glucose (FPG)  $\leq$  270mg/dl (15.0mmol/L) at the enrolment visit.

Note: At Week -2 (Visit 1), a qualification check will be performed and patients will be excluded, if their FPG is >270mg/dl. A re-test will be permitted within 7 days if the initial result was >270mg/dl but <300mg/dl (16.7mmol/L). Patients will be excluded if the mean value of the Week -2 result and the re-test result is >270mg/dl.

- (c) Stable metformin therapy for at least 8 weeks prior to enrolment at a dose of ≥1500mg per day.
- (d) BMI  $\leq 45.0 \text{kg/m}^2$  at Enrolment visit.
- 3. **Age and reproductive status:**
- (a) Men and women, aged  $\geq 18$  years old at time of screening visit.
- (b) For Females Only: Women of childbearing potential (WOCBP) must be using an acceptable method of contraception to avoid pregnancy throughout the study and

for at least 4 weeks after the last dose of study medication in such a manner that the risk of pregnancy is minimized.

- WOCBP must have a negative urine pregnancy test (minimum sensitivity 25IU/L or equivalent units of HCG) within 24 hours prior to the start of investigational product.
- Women are not pregnant or breastfeeding.

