## 5.1.2 Fasting plasma glucose

Blood samples for measurement of FPG will be collected according to the schedule presented in the Study Plan (Table 1). The instructions for collection, processing, packaging and shipping of the samples to central laboratory will be detailed in the laboratory manual.

The results from baseline and onwards will not be reported to the Investigator unless the values meet the defined rescue criteria. In addition, if rescue medication is initiated, the central laboratory FPG value will be reported to the Investigator to ensure proper follow-up of the rescued patient.

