#### Volume of blood

The total blood drawn from each patient over the course of the study will be approximately 100ml.

Table 3 Volume of blood to be withdrawn from each patient

	Sample Volume (ml)						Total Volume (ml)
VISIT	S	V1	V2	V3	V4	V5	
Label	Screen	Enro 1	Randomi sation				
Week	-3	-2	0	6	12	24	
Haematology		2	2		2	2	8 (approx.)
Chemistry a		5	2.5	2.5	2.5	2.5	15 (approx.)
FPG		2	2	2	2	2	10 (approx.)
HbA1c	2		2	2	2	2	10 (approx.)
Hepatitis Panel		3.5					3.5 (approx.)
Total	2	22.5	8.5	6.5	8.5	18.5	67 to 100 b

a. Includes TSH and Free T4

b. Includes a margin for additional visits such as rescue or unscheduled visits.

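### Minor, wrong as written: rescue Table 2 puts the Week 6 visit under both >270 and >240 mg/dL, and on the evident reading the >240 row has no visit at which it can act

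*Protocol*

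**What the plan says.** Protocol 4.4, Table 2, has three rows:

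- Row 1, the Week 6 visit: "FPG >270mg/dL (15.0mmol/L)".
- Row 2, "From Week 6 to Week 12 (Excluding Week 12)": FPG above 240 mg/dL (13.3 mmol/L).
- Row 3, Week 12 to Week 24: FPG above 200 mg/dL (11.1 mmol/L).

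The text below the table applies the rule to a central laboratory value "meeting the lack of glycaemic control criterion at a pre-specified visit". A second sample follows within 3 to 5 days, and the rule is then mandatory: "If the repeat central laboratory FPG value still meets the criterion, the patient must be rescued". A rescued patient stops blinded drug and receives open-label saxagliptin 5 mg plus dapagliflozin 10 mg, with insulin as second line.

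Protocol 1.1 gives the visit schedule: "After randomisation the patients will visit the clinic after 6, 12, and 24 weeks". The study plan (Protocol Table 1) agrees. Under Protocol 5.1.2, FPG results from baseline onwards "will not be reported to the Investigator unless the values meet the defined rescue criteria".

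**The concern.** The table handles one boundary and leaves the other open. The overlap of rows 2 and 3 at Week 12 is removed explicitly. The overlap of rows 1 and 2 at Week 6 is not. For a Week 6 value of, say, 250 mg/dL that is confirmed on repeat, row 1 says no rescue and row 2 says rescue is compulsory.

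The rule decides who leaves blinded treatment. It also decides which FPG values the investigator sees, so a site could not easily notice that the threshold in use differed from the one intended. Too low a threshold moves a patient to open-label therapy early. Too high a threshold leaves a patient with FPG above 240 mg/dL on blinded drug for longer.

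Through those patients the rule reaches three analyses: the exploratory endpoint on rescue or discontinuation for lack of efficacy (SAP 3.4), the HbA1c sensitivity analysis that drops data after rescue (SAP 3.1.6 and 4.2.4.1), and the main hypoglycaemia analysis, which also excludes data after rescue (Protocol 8.5.6).

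**Working it through.** **1. Are the table entries intact?** Taking 18.016 mg/dL per mmol/L (the usual glucose factor, not given in the documents): 270/18.016 = 14.99, 240/18.016 = 13.32 and 200/18.016 = 11.10. These match the printed 15.0, 13.3 and 11.1 mmol/L, so the thresholds were not garbled in the copy.

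**2. Which rows cover each time point, read literally?** Row 1: week = 6. Row 2: 6 ≤ week < 12. Row 3: 12 ≤ week ≤ 24.

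| FPG at Week 6 (mg/dL) | Row 1 (>270) | Row 2 (>240) | Result |
|---|---|---|---|
| 230 | not met | not met | no rescue |
| 250 | not met | met | conflict |
| 280 | met | met | rescue |

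At Week 12 and later only row 3 applies. The conflict is confined to Week 6 values above 240 and up to 270 mg/dL.

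**3. Does either reading leave every row at work?** The study plan places the post-randomisation visits on days 42, 84 and 168, so no scheduled visit lies strictly between Week 6 and Week 12.

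- If row 2 covers Week 6, any value above 270 is also above 240, and row 1 never decides a case.
- If row 1 governs Week 6, row 2 is left with unscheduled samples only. The trigger sentence speaks of a pre-specified visit and does not mention such samples.

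Either way one row does nothing at scheduled visits, so the wording needs repair whichever reading was meant.

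**4. How many patients could be affected?** The documents give no Week 6 FPG distribution, so the following inputs are assumptions: visit and repeat values bivariate normal with common mean m and SD s, correlation r between them, and N = 900 (the planned total). One threshold c is used for both samples.

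- Expected Week 6 values in the disputed band: 900 × [P(X > 240) − P(X > 270)].
- Expected rescues at threshold c: 900 × P(X1 > c and X2 > c).

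For m = 160 and s = 35, the standardised limits are (240 − 160)/35 = 2.286 and (270 − 160)/35 = 3.143. The tail probabilities are 0.01114 and 0.00084, so the band holds 900 × (0.01114 − 0.00084) = 9.3 patients.

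| m, s | Week 6 value >240 to 270 | r | Rescues at >270 | Rescues at >240 | Difference |
|---|---|---|---|---|---|
| 150, 30 | 1.2 | 0.7 | 0.0 | 0.2 | 0.2 |
| 160, 35 | 9.3 | 0.7 | 0.1 | 2.7 | 2.6 |
| 160, 35 | 9.3 | 0.9 | 0.3 | 5.5 | 5.2 |
| 170, 40 | 30.5 | 0.7 | 1.3 | 13.4 | 12.0 |
| 170, 40 | 30.5 | 0.9 | 2.9 | 22.4 | 19.5 |

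Differences are taken before rounding. The central case gives about 3 to 5 of 900, and the whole range is about 0 to 20.

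**The case against.** The strongest reply is that the table has only one sensible reading. A row for a single visit is more specific than a row for an interval, and only Week 6 >270, then >240, then >200 avoids making row 1 redundant. The steps fall in order, and 270 mg/dL is also the entry limit in Protocol 3.1 ("patients will be excluded, if their FPG is >270mg/dl"). This stands: >270 at Week 6 is the evident intent.

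A second reply is that row 2 has a natural use between visits. Protocol 5.2.1 allows extra safety samples at the investigator's discretion, Protocol 5.3.1 recommends daily self-monitoring, and the blood-volume table (Protocol Table 3, footnote b) "Includes a margin for additional visits such as rescue or unscheduled visits". This also stands as a statement of purpose. It means that a reader should not infer that row 2 is surplus and can be deleted, because it is the only threshold stated for that interval. It does not cure the wording, since the trigger sentence still fails to reach those samples.

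Three stronger readings are tempting and are not supported:

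- **That a wrong threshold was used.** The laboratory's alert settings are not in the documents, and nothing shows an error. The counts above compare two rules applied uniformly. They are not a number of patients mishandled, which would be zero if the evident reading was applied.
- **That the primary analysis is compromised.** Protocol 8.5 uses HbA1c values regardless of rescue, so the set of data analysed is the same under either threshold.
- **That the repeat sample has its own ambiguity.** Requiring the repeat to meet the criterion still refers most naturally to the threshold that prompted it.

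Nor is a patient between 240 and 270 mg/dL without protection: Protocol 3.9.1 lets the investigator stop study drug for lack of response or in the patient's interest.

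**Conclusion.** The point holds as a minor error of wording. A mandatory treatment rule gives two answers for a confirmed Week 6 FPG above 240 and up to 270 mg/dL. The reading that resolves this leaves the >240 threshold with no scheduled visit and no stated trigger. The literal overlap is certain from the text; the intent of >270 at Week 6 is a strong inference from the order of the rows and the entry limit.

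The number of patients concerned cannot be known from the documents. About 3 to 5 of 900 is the central figure, and it rests entirely on the assumed mean, SD and correlation; the upper end of the range needs the highest value of all three together. The consequence is the treatment of those few patients and, through them, a small possible effect on the exploratory rescue endpoint, the sensitivity analysis without post-rescue data, and the hypoglycaemia analysis.

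**What to change.** 1. In Protocol Table 2, reword row 2 to: After the Week 6 visit and before the Week 12 visit (excluding Week 6 and Week 12).
2. In the trigger sentence of Protocol 4.4, add unscheduled central-laboratory FPG samples to the pre-specified visits.
3. Confirm that the central laboratory alert at Week 6 is set to >270 mg/dL.

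The cost is a few words in the table, a few in one sentence, and one check of a laboratory setting. The SAP needs no change.

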# 3.9 Discontinuation of investigational product

#### 3.9.1 General discontinuation criteria:

Patients may be discontinued from investigational product (IP) in the following situations:

- 1. Patient decision. The patient is at any time free to discontinue treatment, without prejudice to further treatment.
- 2. Patient experiences an AE or SAE that, in the Investigator's opinion, necessitates discontinuation from study medication.
- 3. The Investigator feels it is in the patient's best interest to discontinue study medication for reasons other than AE. If this decision is made because of an SAE or a clinically significant abnormal laboratory value, appropriate measures are to be taken. The Sponsor or its designee is to be alerted immediately (see Section 6.4).
- 4. Severe non-compliance with the study protocol as judged by the Investigator and/or AstraZeneca
- 5. Incorrectly enrolled patients (see Section 3.4)
- 6. Lack of Therapeutic response

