#### 3.9.2 Study-specific discontinuation criteria:

- 1. Initial and repeat laboratory tests meet any of the following criteria (see Appendix D):
  - ALT and/or AST are >3x ULN and TB >2x ULN
  - ALT and/or AST are >5x ULN for ≥14 consecutive days, at any time after initial confirmatory results
  - ALT and/or AST are >8x ULN
- 2. Pregnancy confirmed by a positive pregnancy test or otherwise verified
- 3. Hypoglycaemia episodes as defined in Section 3.9.3

- 4. Use of (need for) any anti-hyperglycaemic medication other than IP or background metformin or rescue therapy allowed by protocol. Insulin use is permitted in the following situations:
  - For up to 14 days in total during the study and up to 7 continuous days if patients are unable to take oral medications (for example during a gastrointestinal illness)
  - For up to 14 days in total during the study and up to 7 continuous days if there
    is a documented illness or infection that requires additional therapy for
    maintaining glycaemic control
  - For up to 14 days in total during the study and up to 7 continuous days if
    patients have to temporarily stop IP and/or metformin due to recommendations
    made in this clinical study protocol
  - For up to 7 days during hospitalisation. When the reason for hospitalisation is the management of the patient's glycaemic control, treatment with insulin is considered a rescue and is allowed for as long as clinically necessary.
- 5. eGFR <60mL/min/1.73m^2 (by MDRD) confirmed by a repeated central lab measurement within 1 week.

**Note**: Withhold the study medication until results for the retest of eGFR are available ONLY for randomisation visit (For all other visits, there is no need to interrupt the study medication)

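### The confirmed eGFR <60 stopping rule covers only investigational product, so open-label rescue dapagliflozin 10 mg has no written renal rule

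*Protocol*

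**What the plan says.** **Renal rule.** Item 5 of Protocol 3.9.2 stops treatment for eGFR <60 mL/min/1.73m² "confirmed by a repeated central lab measurement within 1 week". Section 3.9, which contains it, is headed "Discontinuation of investigational product". The note to item 5 withholds study medication pending the retest only at randomisation; "For all other visits, there is no need to interrupt the study medication".

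**Rescue.** Under Protocol 4.4 a patient whose FPG exceeds the Table 2 threshold "will be scheduled for a follow-up visit (within 3 to 5 days) to obtain a second central laboratory FPG value". Then: "If the repeat central laboratory FPG value still meets the criterion, the patient must be rescued". On the treatment itself, "rescued patients will be given open-label antidiabetic rescue medication (Saxagliptin 5mg and Dapagliflozin 10 mg as a first line", with "Insulin as a second line at Investigators discretion" as the alternative. The synopsis and 7.9.2 name the same first-line tablets, and Table 6 lists dapagliflozin 10 mg. Section 7.1 places these tablets among the non-IP medications.

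**Monitoring.** Table 1 schedules eGFR at Weeks 6, 12 and 24 and rescue dispensing at Weeks 6 and 12. Section 4.5 includes eGFR among the Rescue Visit procedures, which 4.4 requires before the tablets are given. Table 4 says that eGFR results go to the sites.

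**Rationale.** The Version 4.0 entry in the version history explains the note to item 5: dapagliflozin is contraindicated below an eGFR of 60.

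**The concern.** The sponsor uses one renal threshold to keep patients out of the trial (exclusion 4a) and to stop the blinded tablets, which contain dapagliflozin 5 mg or its placebo. The same threshold is not written for the open-label tablets, which certainly contain dapagliflozin, and at 10 mg. Rescue moves a patient from a product that has a renal stop to one that has none.

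This is a matter of patient safety. If the text is followed literally, a patient with confirmed eGFR <60 can be kept on, or in a narrower case started on, the drug that the version history calls contraindicated at that level. Whether that happens depends on the investigator noticing the reported eGFR and acting on it.

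**Working it through.** **1. Does item 5 reach the rescue tablets?** Three texts bear on this.
- The heading of 3.9 limits the section to IP.
- Section 7.1 names saxagliptin 5 mg and dapagliflozin 10 mg as non-IP when used for rescue, and Table 5 does not list dapagliflozin 10 mg.
- The note to item 5 speaks of study medication. Section 7.6 uses that term broadly enough to include more than IP. However, 4.4 has the rescued patient start rescue medication and discontinue study medication, and footnote k of Table 1 lists rescue medication separately.

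Read together, item 5 does not cover the rescue tablets.

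**2. Is there an eGFR condition elsewhere?** None appears in the synopsis, 4.4 with Table 2, 4.5, 7.3 with Table 6, 7.9, 7.9.2 or the SAP. Of the protocol appendices only the titles were available, and none suggests a renal rule.

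**3. Main case: low eGFR during rescue.** Take a patient on rescue whose eGFR is first low at Week 12. Visit days come from Table 1: Week 12 is day 84, Week 24 is day 168, and each has a ±7-day window.
- Nominal: 168 − 84 = 84 days.
- Shortest: (168 − 7) − (84 + 7) = 70 days.
- Longest: (168 + 7) − (84 − 7) = 98 days.

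The same gap applies when the first low value is on the Rescue Visit sample. If item 5 did apply, exposure after a first low result would be at most 7 days plus laboratory turnaround.

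**4. Narrower case: both confirmations at about the same time.** Suppose a Week 12 visit gives both a low eGFR and a high FPG. The FPG repeat falls on days 3 to 5 and the eGFR repeat by day 7. The eGFR repeat can coincide with the FPG repeat (gap 0 days) or follow it by up to 7 − 5 = 2 or 7 − 3 = 4 days. Item 5 then stops the blinded tablets, which rescue is stopping anyway, and says nothing about the replacement.

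Time remaining to Week 24, before turnaround:
- Nominal: 84 − 5 = 79 to 84 − 3 = 81 days.
- With visit windows: 70 − 5 = 65 to 98 − 3 = 95 days.

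Laboratory turnaround and scheduling of the Rescue Visit shorten this. An assumed 0 to 7 days would make the nominal range 79 − 7 = 72 to 81 days.

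**5. Dose.** 10 / 5 = 2 times the randomised dapagliflozin dose, or 0 to 10 mg for a patient from the saxagliptin arm.

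**6. Number of patients.** The documents give no rescue rate and no renal discontinuation rate, so no count can be computed.

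**The case against.** The strongest reply is that the protocol already protects these patients, and much of it stands.

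- **Renal function is checked around rescue.** eGFR is drawn at the Rescue Visit before the tablets are given. A reader might infer that rescue starts with no renal sample; that is wrong. What is missing is a rule to act on the result.
- **Sites see the result.** Table 4 has eGFR reported to them. Section 5.2 requires investigators to review safety laboratory reports and follow clinically significant abnormalities. Section 6.4.1 lists renal impairment as an event of special interest.
- **Insulin is available.** A reader might infer that a patient with known low eGFR must be given dapagliflozin 10 mg. The documents do not go that far. What is mandatory is rescue. Section 4.4 and the synopsis allow insulin at the investigator's discretion without requiring that the tablets fail first, and 3.9.2 and 7.9 treat insulin during hospitalisation for glycaemic control as rescue. The doubt comes from the second-line label and from 7.9.2, which mentions other therapy only after rescue has failed.
- **Contraindications are mentioned.** Section 7.9 carries the entry medication restrictions into the study, and exclusion 10(a) refers to the investigator brochures and local labels. But 10(a) is an entry criterion and states no on-study action on eGFR.

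A further tempting reading is that patients already taken off IP for low eGFR will later be rescued with 10 mg. They do stay on the visit schedule (3.9.4), but 4.4 says that "patients may be eligible for treatment with open-label rescue medication (see Table 6) to replace their blinded treatment regimen", and such a patient has no blinded regimen to replace. The text does not settle this, and the point does not depend on it. Without that patient, the case at the start of rescue is narrow: if eGFR is confirmed earlier, the patient is already off IP; if later than dispensing, it becomes the main case.

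The note to item 5 also lets blinded treatment continue while a retest is pending after randomisation, so the documents give no basis for asking for an automatic hold.

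**Conclusion.** The gap is real and should be closed. Item 5 applies to IP only, and no written rule requires a retest or stops open-label dapagliflozin 10 mg when a rescued patient's eGFR is or falls below 60. That main case runs for 84 days nominally from Week 12 to Week 24 (70 to 98 with windows). The narrower case, with both confirmations at about the same time, runs for 79 to 81 days nominally after a Week 12 rescue (65 to 95 with windows), before turnaround.

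These are calendar intervals. They assume that the patient stays on the tablets to Week 24 and that the site does not act on the eGFR it receives, so they are upper bounds and not expected exposure. The number of patients is unknown and likely small, because entry excludes eGFR <60. No endpoint or analysis is affected. The word contraindicated comes from the version history, where it explains a note that is still in the current text.

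**What to change.** 1. State in 3.9.2 that item 5 (repeat within 1 week, stop if confirmed) also applies to open-label dapagliflozin.
2. Add to 4.4, 7.9.2 and the synopsis: *Patients with confirmed eGFR <60 mL/min/1.73m² must not start or continue open-label dapagliflozin and may receive insulin as first-line rescue.*

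An optional convenience is to take any pending eGFR retest at the 3 to 5 day FPG visit, so that the result can be known before tablets are dispensed.

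The cost is a short amendment and one extra retest for the few rescued patients with a low eGFR. Table 3 already allows a blood-volume margin for rescue or unscheduled visits. Patients still on IP need no new test, because item 5 already requires their retest within 1 week.
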